9.5 Electrocardiogram Data

All ECG analyses are made using observed data. Baseline is defined as average of ECG measurements at baseline visit as specified in [Section 5.2](#). Last visit for each phase is defined as average of ECG measurements at last visit as specified in [Section 5.2](#). Missing ECG data will not be imputed. For the calculation of QT correction by heart rate, QTc is missing only if all three consecutive beats are unreadable. If there is at least 1 beat available in the lead, the data are included in the analysis. For each ECG, QT and RR

intervals from three consecutive complexes (representing three consecutive heart beats) are measured manually. The QT correction is performed on beat-to-beat basis. The mean of ratios (beat-to-beat) is calculated by $(QT_{c1} + QT_{c2} + QT_{c3})/3$ using each QT-RR pair: (QT1, RR1), (QT2, RR2) and (QT3, RR3). The corrected QT intervals for QT_{cB}, QT_{cF}, and QT_{cN} are defined as follows:

- QT_{cB} is the length of the QT interval corrected for heart rate by Bazett's formula: $QT_{cB} = QT / (RR)^{1/2}$.
- QT_{cF} is the length of the QT interval corrected for heart rate by Fredericia's formula: $QT_{cF} = QT / (RR)^{1/3}$.
- QT_{cN} is the length of the QT interval corrected for heart rate by the FDA Neuropharm Division formula: $QT_{cN} = QT/(RR)^{0.37}$.

Potentially clinically relevant ECG abnormalities will be listed by subject. Criteria for identifying ECG measurements of the potentially clinically relevance are provided in [Appendix 3](#). The incidences of abnormal ECGs of potential clinical relevance based on the observation at the scheduled and the unscheduled post-baseline visits will be tabulated the safety samples. Descriptive statistics of change from baseline in ECG intervals of PR, QRS, RR, QT, QT_{cB}, QT_{cF}, and QT_{cN} will be presented at each scheduled trial week and last visit for the safety samples.

In summarizing the incidence of abnormalities, a patient must have had an evaluation that meets abnormality criteria by the end of trial phase. Incidence rate is calculated as the number of patients having at least 1 abnormality within the corresponding study phase divided by the number of patients who are both exposed to study medication and have an on-treatment evaluation within the same study phase.

If ECG assessments are repeated for the same trial week, the last repeat values will be used for production of mean change from baseline. This is accomplished by sorting patient data by visit date and visit time (if applicable) within the same visit identification.

9.6 Other Safety Data

9.6.1 Extrapyramidal Symptoms

EPS rating scales include the Simpson-Angus Scale (SAS), Barnes Akathisia Rating Scale (BARS) and Abnormal Involuntary Movement Scale (AIMS). The following variables will be analyzed: 1) Change from Baseline in SAS Total Score, 2) Change from Baseline in BARS Global Score, 3) Change from Baseline in AIMS Movement Rating Score (i.e., total of item 1 to 7).

The SAS total score (range 10-50) is the sum of the rating scores for 10 items from the SAS panel in the eCRF. The BARS global score (range 0-5) is derived from the global

clinical assessment of akathisia from the BARS panel in the eCRF. The AIMS movement rating score (range 0-28) is the sum of the rating scores for facial and oral moments (i.e., item 1 - 4), extremity movements (i.e. item 5 - 6), and trunk movements (i.e. item 7) from the AIMS panel in the eCRF. A missing value of any item for SAS and AIMS movements scale could result in a missing SAS total score or AIMS movement rating score.

Changes from baseline in EPS scale scores will be summarized by trial week for the safety samples. EPS rating scale scores will be presented for OC datasets.

9.6.2 Suicidality

The incidence of suicidality, suicidal behavior and suicidal ideation will be calculated from the potential suicide events recorded on the C-SSRS (children's version) in the single-blind stabilization phase and double-blind randomized withdrawal phase for the safety samples. Suicidality will be assessed based on C-SSRS data. Data for the Baseline Version of the C-SSRS and Since Last Visit Version of the C-SSRS data will be summarized descriptively and presented in a listing.

The baseline version of C-SSRS is administered at the screening visit and the "Since Last Visit" version is administered at all subsequent visits. Baseline and post-baseline C-SSRS data will be summarized to report the incidence of suicidality, suicidal behavior and suicidal ideation. Suicidality is defined as reporting at least 1 occurrence of any suicidal behavior or suicidal ideation. Suicidal behavior is defined as reporting any type of suicidal behaviors. Suicidal ideation is defined as reporting any type of suicidal ideation.

In addition, C-SSRS data collected post-baseline will also be summarized to report the incidence of completed suicide, emergence of suicidal ideation, emergence of serious suicidal ideation, worsening of suicidal ideation and emergence of suicidal behavior. Any completed suicide is considered as complete suicidality. Emergence of suicidal ideation is defined as having no suicidal ideation at screening and baseline and reporting any type of ideation during treatment. Emergence of serious suicidal ideation is defined as having no suicidal ideation at screening and baseline and reporting any type of suicidal ideation with ideation severity rating of 4 or 5 during treatment. Worsening of suicidal ideation is defined as occurring when the most severe suicidal ideation rating during treatment is more severe than its worst rating at screening and baseline. Emergence of suicidal behavior is defined as having no suicidal behavior at screening and baseline and reporting any type of suicidal behavior during treatment.

10 Pharmacokinetic Analyses

None.

11 Pharmacodynamic Analyses

None.

12 Pharmacogenomic Analyses.

None.

13 Interim Analysis

None.

14 Changes in the Planned Analyses

This trial was terminated due to withdrawal of postmarketing commitment, so the interim analysis specified in the protocol was not to be conducted. The descriptive statistics will be provided for all the efficacy endpoints.

Appendix 1 Criteria for Identifying Laboratory Values of Potential Clinical Relevance

Laboratory Tests	Criteria
Chemistry^a	
AST (SGOT)	≥ 3 x ULN
ALT (SGPT)	≥ 3 x ULN
Alkaline phosphatase	≥ 3 x ULN
LDH	≥ 3 x ULN
BUN	≥ 30 mg/dL
Creatinine	≥ 2.0 mg/dL
Uric Acid	
Male	≥ 10.5 mg/dL
Female	≥ 8.5 mg/dL
Bilirubin (total)	≥ 2.0 mg/dL
CPK	≥ 3 x ULN
Prolactin	> ULN
Hematology^a	
Hematocrit	≤ 30 % and decrease of ≥ 3 percentage points from baseline
Hemoglobin	
Male	≤ 11.5 g/dL
Female	≤ 9.5 g/dL
White blood count	≤ 2,800 mm ³ or ≥ 16,000 mm ³
Eosinophils	≥ 10%
Neutrophils	≤ 1.5 THOUS/μL
Platelet count	≤ 75,000/ mm ³
Urinalysis^a	
Protein	Increase of ≥ 2 units
Glucose	Increase of ≥ 2 units
Casts	Increase of ≥ 2 units
Additional Criteria	
Chloride	≤ 90 mEq/L or ≥ 118 mEq/L
Hb1Ac	≥ 7%
Potassium	≤ 3.0 mEq/L or ≥ 5.5 mEq/L
Sodium	≤ 120 mEq/L or ≥ 160 mEq/L
Phosphorous, inorganic	≤ 1.0 mg/dL
Magnesium, serum	≤ 0.7 mEq/L or ≥ 5.0 mEq/L
Calcium	≤ 8.2 mg/dL or ≥ 12 mg/dL
Glucose, Fasting, serum	≥ 115 mg/dL
Total Cholesterol, Fasting	≥ 240 mg/dL
LDL Cholesterol, Fasting	≥ 160 mg/dL
HDL Cholesterol, Fasting	≤ 30 mg/dL
Triglycerides, Fasting	
Male	≥ 160 mg/dL
Female	≥ 120 mg/dL

^a As defined in "Supplementary Suggestions for Preparing an Integrated Summary of Safety Information in an Original NDA Submission and for Organizing Information in Periodic Safety Updates," FDA Division of Neuropharmacological Drug Products draft (2/27/87).

Appendix 2 Criteria for Identifying Vital Signs of Potential Clinical Relevance

Variable	Criterion Value^a	Change Relative to Baseline^a
Heart Rate ^b	> 120 bpm < 50 bpm	≥ 15 bpm increase ≥ 15 bpm decrease
Systolic Blood Pressure ^b	> 180 mmHg < 90 mmHg	≥ 20 mmHg increase ≥ 20 mmHg decrease
Diastolic Blood Pressure ^b	> 105 mmHg < 50 mmHg	≥ 15 mmHg increase ≥ 15 mmHg decrease
Weight	-	≥ 7% increase ≥ 7% decrease

^a In order to be identified as potentially clinically relevant, an on-treatment value must meet the “Criterion Value” and also represent a change from the subject’s baseline value of at least the magnitude shown in the “Change Relative to Baseline” column.

^b As defined in “Supplementary Suggestions for Preparing an Integrated Summary of Safety Information in an Original NDA Submission and for Organizing Information in Periodic Safety Updates,” FDA Division of Neuropharmacological Drug Products draft (2/27/87).

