3.1 Type of Trial

This phase 3b/4 trial is a randomized, double-blind, placebo-controlled trial to evaluate the long-term efficacy of oral aripiprazole in the treatment of pediatric subjects with TD. Subjects, 6 to 17 years of age, are recruited at approximately 70 sites globally. The trial consists of 3 distinct phases: a pretreatment phase, an open-label stabilization phase, and a double-blind randomized withdrawal phase. Screening assessments may occur during 1 or more visits (as needed) and must occur in the clinic. The baseline visit occurs in the clinic, as well the open-label stabilization phase visits on Weeks 1, 2, 4, 8, 12, 14, 16, 18, and 20 and the double-blind, randomized withdrawal phase visits at Weeks 1, 2, 4, 8, and 12. All other visits occur via telephone, web, in-clinic, or other acceptable means of contact. The trial schematic is presented in [Figure 3.1-1](#).

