3.3 Trial Population

3.3.1 Number of Subjects and Description of Population

The trial population includes pediatric subjects, 6 to 17 years of age, meeting the current Diagnostic and Statistical Manual of Mental Disorders, Fifth Edition (DSM-5) diagnostic criteria for TD. It is anticipated that approximately 228 subjects will be enrolled in the open-label stabilization phase from approximately 70 sites worldwide in order to randomize approximately 114 subjects into the double-blind randomized withdrawal phase.

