9.4 Vital Sign Data

Vital signs include body temperature, heart rate, systolic blood pressure and diastolic blood pressure in supine and sitting position. In addition, body weight and waist circumference are measured. Potentially clinically relevant vital sign abnormalities will be listed by subject. Criteria for identifying vital signs of the potential clinical relevance are provided in [Appendix 2](#). Incidences of clinically relevant vital signs abnormalities based on the observation from the scheduled and unscheduled post-baseline visits will be tabulated safety samples. In addition to weight, BMI and waist circumference, vitals sign parameters at each trial week, and change from baseline at the post-baseline trial weeks will be summarized using descriptive statistics for the safety samples in the corresponding phases.

If vital sign assessments are repeated for the same trial week, the last repeat values will be used for production of mean change from baseline. This is accomplished by sorting patient data by visit date and visit time (if applicable) within the same visit identification.

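### The high blood-pressure flags (systolic > 180, diastolic > 105 mmHg) are fixed for ages 6 to 17, so large individual rises such as 95 to 175 mmHg are not counted

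*SAP*

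**What the plan says.** SAP 3.3.1 describes one population: "The trial population includes pediatric subjects, 6 to 17 years of age". SAP Appendix 2, which matches Protocol Appendix 1, lists the limits with no strata for age, sex or height:

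- Systolic: criterion values "> 180 mmHg < 90 mmHg", with changes "≥ 20 mmHg increase ≥ 20 mmHg decrease".
- Diastolic: criterion values "> 105 mmHg < 50 mmHg", with changes "≥ 15 mmHg increase ≥ 15 mmHg decrease".
- Heart rate: criterion values "> 120 bpm < 50 bpm", with a change of at least 15 bpm in the same direction.
- Weight: a change of at least 7% either way, with no absolute limit.

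Footnote a of the appendix requires the criterion value and the change to be met together. SAP 9.4 states the use: "Potentially clinically relevant vital sign abnormalities will be listed by subject". It also plans incidence tables from scheduled and unscheduled visits, which are CT-11.2 (Randomized Safety Sample) and CT-17.2 (Open-Label Safety Sample) in SAP Appendix 4. Separately, SAP 9.4 plans descriptive statistics for values and changes from baseline by trial week (CT-11.1.1 and CT-17.1.1).

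**The concern.** Safety and tolerability are the trial's secondary objective, and the subjects are children and adolescents. The incidence tables exist to count individuals with notable vital-sign changes. For rises in blood pressure, the absolute limit sits so far above the values expected in this age range that the change condition hardly matters: the limit decides almost every case, and almost no case reaches it. A zero in the high systolic or high diastolic cell could then be read as reassurance, although the rule would give a zero even if several children had large rises. SAP 8.1.1 and Section 14 reduce efficacy to descriptive statistics after early termination, so the safety tables are a larger share of what the final report offers.

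**Working it through.** The documents give no expected incidence for these flags, so there is no plan figure to reproduce. The check has a part that follows from the text alone and a part that rests on assumptions.

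**1. The rule itself (no assumptions).** Let b be the baseline and v the on-treatment value, in whole mmHg. A high systolic flag needs v > 180 and v − b ≥ 20. A high diastolic flag needs v > 105 and v − b ≥ 15. The smallest rise that is flagged is therefore

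- systolic: the larger of 20 and 181 − b;
- diastolic: the larger of 15 and 106 − b.

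| Measure | Baseline | On treatment | Rise | Flagged? | Smallest flagged rise from this baseline |
|---|---|---|---|---|---|
| Systolic | 95 | 175 | 80 | No (175 is not > 180) | 181 − 95 = 86 |
| Diastolic | 55 | 100 | 45 | No (100 is not > 105) | 106 − 55 = 51 |
| Diastolic | 60 | 105 | 45 | No (105 is not > 105) | 106 − 60 = 46 |

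The stated increments decide the outcome only from a baseline of 181 − 20 = 161 mmHg systolic or 106 − 15 = 91 mmHg diastolic upward. Below that, the absolute limit alone decides.

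**2. The other rows (no assumptions).** Systolic 110 to 88 is flagged low, diastolic 65 to 48 is flagged low, heart rate 100 to 121 is flagged high, and weight 30.0 to 32.1 kg (+7%) is flagged. These rows are reachable.

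**3. Size of the gap in the high systolic cell (assumed values, not in the documents).** Take resting systolic pressure as normal with mean 95, 105 or 115 and SD 10, and suppose every child rises by 30 mmHg. The chance that one reading exceeds 180 is P(Z > (180 − mean − 30)/10):

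- mean 95: P(Z > 5.5) = 1.9 × 10⁻⁸
- mean 105: P(Z > 4.5) = 3.4 × 10⁻⁶
- mean 115: P(Z > 3.5) = 2.3 × 10⁻⁴

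At the top of this range, 2.3 × 10⁻⁴ × 228 planned subjects ≈ 0.05 flagged readings per visit. Over the nine open-label clinic visits after baseline (Weeks 1, 2, 4, 8, 12, 14, 16, 18, 20) this is about 0.05 × 9 ≈ 0.5 readings, at one reading per visit.

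**4. All rows with no drug effect (simulation on assumed distributions, 5 or 9 post-baseline visits).** Share of subjects flagged at least once:

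| Row | Assumed mean; between-subject SD; within-subject SD | High | Low |
|---|---|---|---|
| Systolic | 100–115; 9; 6–10 | 0.0% | 0.4%–25% |
| Diastolic | 60–70; 7; 5–9 | 0.0%–0.7% | 0.6%–33% |
| Heart rate | 75–95; 10; 7–12 | 0.03%–20% | 0.02%–20% |

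By a normal calculation, a weight gain of at least 7% occurs in 5%–50% if the mean gain is 2%–7% with SD 3–5 points. Only the two high blood-pressure cells are near empty.

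**5. Can the mean-change tables stand in?** One child with +80 mmHg moves the mean by 80/38 ≈ 2.1 mmHg in an arm of 38, and by 80/228 ≈ 0.35 mmHg in 228 subjects. A shift in the whole group would be visible. A few large individual rises would not be counted.

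**6. What change-only rows would pick up by chance.** With no drug effect and within-subject SD s, the change between two readings has SD s√2.

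- Systolic, s = 6 to 10: P(Z > 20/(s√2)) = P(Z > 2.36) to P(Z > 1.41), or 0.9% to 7.9% per reading.
- Diastolic, s = 5 to 9: P(Z > 15/(s√2)) = P(Z > 2.12) to P(Z > 1.18), or 1.7% to 11.9% per reading.

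The share of subjects with at least one such reading over several visits would be higher. For contrast, if every child rose by 30 mmHg, the systolic row would flag P(Z > (20 − 30)/(s√2)), or 76% (s = 10) to 88% (s = 6) of readings.

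**The case against.** Much can be said for the plan. The limits are prespecified, agree between protocol and SAP, and are attributed in footnote b to an FDA division draft. The criteria identify values of potential relevance. The note to the exclusion criteria in Protocol 3.4.3 presents them as an aid to investigator judgment, and no passage calls a rise to 175 mmHg irrelevant. Such a value can still be reported as an adverse event. Weight gain, which Protocol 1.2.2 names among the main drug-related events in the earlier extension trial, has a row with no absolute limit. A uniform rise of 30 mmHg would be plain in CT-11.1.1 and CT-17.1.1. The trial has also ended early, and the appendix figures above depend partly on assumed distributions.

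Most of this stands, and it limits the point. A reader might infer that the vital-sign incidence tables as a whole are close to empty by construction. The documents do not support that: the low blood-pressure, heart-rate and weight rows can all fill. A reader might also infer that no other output would show such a child. That cannot be established, because the SAP's list of patient data listings is incomplete in the available text. Nor is the match between the diastolic flag and the diastolic exclusion limit (both > 105 mmHg) a contradiction.

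The objection does not supply a count of individual children with large rises. Mean changes dilute them, and adverse-event reporting depends on the investigator's judgment.

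**Conclusion.** The point holds for the two high blood-pressure cells of CT-11.2 and CT-17.2 and for the flagged-value listing built on the same rule. That 95 to 175 mmHg systolic and 55 to 100 mmHg diastolic go uncounted follows from Appendix 2 alone. That the cells will be near zero rests on assumed pressures for this age range, but the margin is wide: even with every child raised by 30 mmHg, about 0.05 flagged readings per visit or fewer are expected in 228 subjects. That number is planned enrollment, so the count under early termination may be smaller still. A zero in these cells should not be read as evidence that no child had a large rise. The point concerns descriptive safety reporting. It does not affect the efficacy results or the management of any subject.

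**What to change.** Keep every existing row, so that the cited criteria are still reported. Add to CT-11.2, CT-17.2 and the accompanying listings change-only incidence rows for blood pressure, using the increments already in Appendix 2: a rise of at least 20 mmHg systolic and a rise of at least 15 mmHg diastolic. Measure each rise from the phase-specific baseline in SAP 5.2 and report the rows by treatment group in the randomized phase. State that both readings must be taken in the same position, and settle which positions apply: the protocol's visit schedule takes sitting and standing readings, while SAP 9.4 names supine and sitting.

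The cost is programming on data already collected. The downside is that the rows will include isolated fluctuations, at roughly the per-reading rates in step 6. In the randomized phase the placebo arm gives a reference for these; in the open-label phase there is none, and a footnote should say so. An age-referenced blood-pressure summary is optional. It would need an external reference standard, which the sponsor would choose.

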Appendix 3 Criteria for Identifying ECG Measurements of Potential Clinical Relevance

Variable	Criterion Value ^a	Change Relative to Baseline ^a
Rate		
Tachycardia	≥ 120 bpm	increase of ≥ 15 bpm
Bradycardia	≤ 50 bpm	decrease of ≥ 15 bpm
Rhythm		
Sinus tachycardia ^b	≥ 120 bpm	increase of ≥ 15 bpm
Sinus bradycardia ^c	≤ 50 bpm	decrease of ≥ 15 bpm
Supraventricular premature beat	all	not present → present
Ventricular premature beat	all	not present → present
Supraventricular tachycardia	all	not present → present
Ventricular tachycardia	all	not present → present
Atrial fibrillation	all	not present → present
Atrial flutter	all	not present → present
Conduction		
1° atrioventricular block	PR ≥ 0.20 second	increase of ≥ 0.05 second
2° atrioventricular block	all	not present → present
3° atrioventricular block	all	not present → present
Left bundle-branch block	all	not present → present
Right bundle-branch block	all	not present → present
Pre-excitation syndrome	all	not present → present
Other intraventricular conduction block ^d	QRS ≥ 0.12 second	increase of ≥ 0.02 second
Infarction		
Acute or subacute	all	not present → present
Old	all	not present → present ≥ 12 weeks post trial entry
ST/TMorphological		
Myocardial Ischemia	all	not present → present
Symmetrical T-wave inversion	all	not present → present
Increase in QTc	QTc ≥ 450 msec (males)	≥ 10% increase
	QTc ≥ 470 msec (females)	≥ 10% increase

^a In order to be identified as potentially clinically relevant, an on-treatment value must meet the “Criterion Value” and also represent a change from the subject’s baseline value of at least the magnitude shown in the “Change Relative to Baseline” column.

^b No current diagnosis of supraventricular tachycardia, ventricular tachycardia, atrial fibrillation, atrial flutter, or other rhythm abnormality.

^c No current diagnosis of atrial fibrillation, atrial flutter, or other rhythm abnormality.

^d No current diagnosis of left bundle branch block or right bundle branch block.

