3.7.3.4 Electrocardiogram Assessments

A standard 12-lead ECG will be recorded at the visits designated in [Table 3.7-1](#) and [Table 3.7-2](#). It will be done at rest, with the subject lying down for approximately 5 minutes before the ECG is obtained. A central ECG service will be utilized for reading all ECGs in order to standardize interpretations for the safety analysis. The ECG will be evaluated at the investigational site to determine the subject's eligibility and to monitor safety during the trial. The principal investigator or qualified designee will review, sign, and date each ECG reading, noting whether or not any abnormal results are of clinical significance. The ECG will be repeated if any results are considered to be clinically significant.

Based on the QTcF correction, a subject will be excluded from the trial if the correction is ≥ 450 msec (males) or ≥ 470 msec (females). Subjects with clinically significant ECG findings at screening may enter the open-label stabilization phase only after the screening ECG is repeated and determined by the investigator prior to treatment to have no abnormalities that are clinically significant.

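### The joint QTc criterion leaves uncounted any on-treatment value from 450 msec (males) or 470 msec (females) up to just below 1.10 × baseline, when the phase baseline exceeds about 409 or 427 msec

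*SAP*

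**What the plan says.** SAP Appendix 3 has one QTc row, headed as an increase in QTc. Its criterion values are "QTc ≥ 450 msec (males") and "QTc ≥ 470 msec (females"), each paired with a rise of at least 10%. Footnote a makes the two parts joint. It says "In order to be identified as potentially clinically relevant, an on-treatment value must meet the" listed limit. Passing the limit is not enough by itself, however: the result must "also represent a change from the subject’s baseline value of at least the magnitude shown", here 10%. Protocol Appendix 3 has the same rule.

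SAP 9.5 builds its abnormality outputs on that appendix. "Potentially clinically relevant ECG abnormalities will be listed by subject". As for counts, "The incidences of abnormal ECGs of potential clinical relevance based on the observation at the scheduled and the unscheduled post-baseline visits will be tabulated". In the table index these are CT-12.3.1 (listing), CT-12.2 (incidence, Randomized Safety Sample) and CT-18.2 (incidence, Open-Label Safety Sample). The other QTc output that SAP 9.5 plans is "Descriptive statistics of change from baseline in ECG intervals of PR, QRS, RR, QT" and the three corrected QT intervals (QTcB, QTcF, QTcN), shown in CT-12.1 and CT-18.1.

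Protocol 3.7.3.4 uses the same numbers at entry: under QTcF, "a subject will be excluded from the trial if the correction is ≥ 450 msec (males) or ≥ 470 msec (females"). SAP 5.2, which SAP 9.5 cites for ECGs, takes the open-label baseline from the last data before the first open-label dose, and the double-blind baseline from the last open-label visit.

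**The concern.** When both parts are required, the absolute limit decides only for subjects with a low baseline. Once 1.10 × baseline exceeds the limit, the relative rule alone decides. A child may then reach, on treatment, a QTc at which the protocol would not have admitted that child, and the incidence tables would show no QTc abnormality. The rule is least sensitive in eligible children who start closest to the limit.

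Safety and tolerability are the trial's secondary objective, and SAP 8.1.1 and 14 reduce the efficacy analysis to descriptive statistics after early termination. Counts and listings of individual abnormal values therefore carry much of the safety information. A mean change in QTc does not show who passed a given level.

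**Working it through.** The plan states no derived figure to reproduce, so the check is direct arithmetic on its criteria.

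**Inputs.** Limit L = 450 msec (males) or 470 msec (females), required rise 10%, both parts needed (SAP Appendix 3, footnote a). Entry limits on QTcF are the same numbers (Protocol Table 3.4.3-1, item 20h, and 3.7.3.4). Baseline B is set separately for each phase (SAP 5.2).

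**Step 1: effective threshold.** A value is flagged if QTc ≥ L and QTc ≥ 1.10 × B, that is, if QTc ≥ max(L, 1.10 × B).

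**Step 2: break-even baseline.** The relative rule takes over when B > L / 1.10.
- Males: 450 / 1.10 = 409.1 msec.
- Females: 470 / 1.10 = 427.3 msec.

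**Step 3: missed band.** Values from L up to just below 1.10 × B are not flagged. The width is max(0, 1.10 × B − L).

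| Sex | Baseline (msec) | Flagged from (msec) | Missed band (msec) |
|---|---|---|---|
| Male | 400 | 450.0 | 0 |
| Male | 410 | 451.0 | 1.0 |
| Male | 420 | 462.0 | 12.0 |
| Male | 440 | 484.0 | 34.0 |
| Male | 449 | 493.9 | 43.9 |
| Female | 428 | 470.8 | 0.8 |
| Female | 440 | 484.0 | 14.0 |
| Female | 469 | 515.9 | 45.9 |

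In whole milliseconds, 449 and 469 are the highest eligible entry values. Examples based on entry values belong to the open-label table, CT-18.2. For CT-12.2 the relevant baseline is the last open-label visit.

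**Step 4: one case each side of the line.** A male going from 420 to 455 msec rises by 455 / 420 − 1 = 8.3% and is not flagged, although he is above 450. A male going from 410 to 480 msec rises by 480 / 410 − 1 = 17.1% and is flagged.

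**Step 5: across the two phases.** Take, as an illustration, a male at 400 msec at entry, 445 at randomization and 460 in the double-blind phase.
- Open-label: 445 / 400 − 1 = 11.3%, but 445 < 450, so not flagged.
- Double-blind: 460 ≥ 450, but 460 / 445 − 1 = 3.4%, so not flagged. The threshold is now 1.10 × 445 = 489.5 msec.
- Against entry: 460 / 400 − 1 = 15%. With the entry value as baseline the threshold would be max(450, 440) = 450, and 460 would be flagged.

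The documents state no QTc cap for the randomization visit, so the double-blind baseline, and with it the missed band, could exceed the entry-based figures above.

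**The case against.** The strongest reply is that the rule is deliberate. It appears identically in both documents, and value plus change is the convention for the rate, PR and QRS rows and for heart rate and blood pressure. It separates change on treatment from a high starting value. This stands: there is no contradiction, and the joint criterion should be kept. It does not close the gap, because the double-blind baseline is itself an on-drug value and can absorb an earlier rise.

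Three stronger readings are tempting, and the documents do not support them.

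- *Every on-treatment value above the limit is lost for subjects with baselines above 409/427 msec.* Only the band up to just below 1.10 × baseline is lost. Close to the break-even that is about 1 msec.
- *The plan breaches its own on-treatment limit.* The 450/470 msec QTcF figures govern eligibility. In Protocol 3.7.3.4 the sentence is followed by the rule for findings at screening, and the ECG footnote to the double-blind schedule (Table 3.7-2) gives no QTc limit. Neither document requires an on-treatment value at that level to be counted by itself.
- *These values are invisible.* They enter the change-from-baseline summaries, and under Protocol 3.7.3.4 each ECG is reviewed and signed at the site with clinical significance noted. The visible listing index stops at PDATA-3.1, so a full by-subject ECG listing cannot be ruled out. Such a listing would still not give a count.

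It is also fair to say that the effect may be nil. The documents give no baseline QTc distribution, so the number of subjects in the band could be zero.

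**Conclusion.** The point holds as a limitation of the safety summary. For a male with a phase baseline above 409 msec or a female above 427 msec, on-treatment QTc from 450 (470) msec up to just below 1.10 × baseline is left out of CT-12.2, CT-18.2 and CT-12.3.1, and no other visible output counts it. The band runs from about 1 msec just above the break-even to 43.9 msec (males) and 45.9 msec (females) at the highest eligible entry baselines. A subject can pass the limit across the two phases and be flagged in neither.

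This rests on two assumptions. First, Appendix 3 says only QTc, while SAP 9.5 defines three corrections. The comparison with the entry limits assumes that QTcF is meant; under another correction the 449/469 msec ceiling on the entry baseline would not apply. Second, the phase baselines follow SAP 5.2 as written. The number of subjects affected cannot be derived from the documents. The matter is minor, but cheap to put right.

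**What to change.** In SAP 9.5, add the incidence of any post-baseline QTcF of at least 450 msec (males) or 470 msec (females), regardless of change from baseline. Show it as a separate row in both CT-12.2 and CT-18.2, and add a matching flag to the CT-12.3.1 listing. Name QTcF as the correction for the new row. Keep the joint criterion as its own row, so that values which also represent a 10% rise remain distinguishable.

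No new data are needed, since QTcF is already derived under SAP 9.5. The cost is one row in each of two tables and one listing flag. The downside is that some small changes from a high baseline will be listed; the joint-criterion row beside it puts these in context. This is a reporting change only and implies no rule for managing subjects.
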